### **Objective**

To determine and compare invasive ventilation settings and parameters in COVID–19 patients in the Netherlands, and to determine associations with clinical outcomes.

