### **Hypotheses**

Invasive ventilation settings and parameters vary between intensive care units (ICUs) in hospitals in the Netherlands; certain ventilator settings have an independent association with duration of ventilation in COVID–19 patients.

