#### **2.1.2 Secondary objective**

To determine whether certain ventilation settings have an independent association with duration of ventilation.

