#### **2.2.2 Secondary hypothesis**

Certain ventilation settings impact duration of ventilation.

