#### 5.1.2 Secondary study parameters

- Number of ventilation-free days and alive at day 28 (VFD-28);
- Duration of ventilation in survivors;
- Use of prone positioning;
- Use of recruitment maneuvers;
- Incidence of acute kidney injury (AKI);
- Duration of ICU stay;
- Duration of hospital stay;
- ICU mortality;
- Hospital mortality;
- 28-day mortality; and
- 90-day mortality.

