### 5.3 Study procedures

Patients will be included by the attending clinician. Participating centers will be visited by researchers to collect data of included patients.

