Mixed–effect multivariable logistic or linear regression model will be used to identify factors independently associated with major outcomes, like death and VFD–28. Subanalyses are planned to investigate differences in ventilation practice and outcomes in the following prespecified subgroups: women versus men, and patients categorized by the body mass index.

All analyses will be conducted in R v.3.6.0 and a p value < 0.05 will be considered statistically significant.

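### The secondary objective concerns duration of ventilation, but its endpoints either combine death with duration or condition on survival, and no named model treats death as a competing event

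*Combined protocol and SAP*

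**What the plan says.** Section 2.1.2 gives the secondary objective: "To determine whether certain ventilation settings have an independent association with duration of ventilation". Section 2.2.2 gives the hypothesis: "Certain ventilation settings impact duration of ventilation". The Summary repeats it under Hypotheses: "certain ventilator settings have an independent association with duration of ventilation". The Summary's Objective is wider and also aims "to determine associations with clinical outcomes".

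Of the secondary parameters in Section 5.1.2, two carry duration: "Number of ventilation-free days and alive at day 28 (VFD-28" and "Duration of ventilation in survivors". ICU, hospital, 28-day and 90-day mortality are listed separately. The plan does not spell out how deaths are scored in VFD-28, although its name points to zero. It does not state the day on which survival is judged for the survivor endpoint.

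Section 7 requires mixed models with a random hospital effect throughout. For outcomes it adds: "Mixed–effect multivariable logistic or linear regression model will be used to identify factors independently associated with major outcomes, like death and VFD–28". It names no time-to-event or competing-event method. The limitation it admits is that many patients will still be ventilated at the first analysis step. It says nothing there about death.

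**The concern.** A patient who dies on the ventilator has no observed time to extubation, and Section 1.1 calls mortality in ventilated patients considerable. VFD-28 lets such deaths pull the score down. Duration in survivors drops them, so the compared groups are selected by something that happens after the setting was chosen. Either way, a setting that changes mortality and leaves the rate of liberation alone can appear to change duration. The two endpoints can even disagree: fewer ventilator-free days looks like harm, while shorter ventilation in survivors looks like benefit. The plan has no analysis of extubation itself to help a reader tell these apart. At stake is how the answer to the secondary objective is read. The wider aim of associations with clinical outcomes is served by death and VFD-28 as planned.

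**Working it through.** The plan gives no effect size, event rate or power for this objective, so there is no figure to reproduce. The check asks how far each measure moves when a setting affects death only.

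**Inputs.** From the plan: at least 1,000 patients (Section 4.4), follow-up to day 90 for the second step and a 0.05 significance level (Section 7). Assumed: a binary setting with 500 per group, no covariates, deaths scored 0 in VFD-28, and all event rates.

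**Case A, competing constant hazards.** Liberation hazard le = 0.05/day in both groups; death hazard ld = 0.02 versus 0.0313/day; s = le + ld, that is 0.07 versus 0.0813.

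- 28-day death = (ld/s)(1 - exp(-28s)): 0.2857 × 0.859 = 24.5% versus 0.385 × 0.897 = 34.5%.
- E[VFD-28] = le[28/s - (1 - exp(-28s))/s²]: 0.05 × (400.0 - 175.3) = 11.2 versus 0.05 × (344.4 - 135.8) = 10.4. The shift is **-0.8 days** (-0.7 to -0.9 for le = 0.04 to 0.06).
- Mean duration if liberated by day 90 = 1/s - 90·exp(-90s)/(1 - exp(-90s)): 14.29 - 0.17 = 14.12 versus 12.30 - 0.06 = 12.24. The shift is **-1.9 days**.
- The choice of survivors matters: the shift is -1.1 days in day-28 survivors and -0.6 days in those liberated by day 28.

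**Case B, death independent of latent duration.** 25% versus 35% die while ventilated (mean time to death 12 days); the others are liberated at L, exponential with rate le.

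- E[(28 - L)+] = 28 - (1 - exp(-28le))/le = 28 - 0.7534/0.05 = 12.93. The VFD-28 shift is -0.10 × 12.93 = **-1.3 days** (-1.1 to -1.4 for le = 0.04 to 0.06).
- Survivor duration shift: **0**.

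**Share of simulated studies with p < 0.05** (le = 0.05). The extubation hazard is a log-rank test with death and day 90 as censoring.

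| Measure | 10-point gap: A | 10-point gap: B | 5-point gap: A | 5-point gap: B |
|---|---|---|---|---|
| VFD-28 | 21% | 51% | 9% | 17% |
| Duration, liberated by day 90 | 46% | 5% | 16% | 5% |
| Cause-specific extubation hazard | 5% | 24% | 5% | 10% |
| 28-day death | 93% | 90% | about 40% | about 40% |
| VFD-28 significant, death not | 0.2% | 1.9% | 1.4% | 4.9% |

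In case B the extubation-hazard figure at the 10-point gap runs from 13% to 47% for a mean time to death of 8 to 20 days. With 20 hospitals of 50 patients, an assumed hospital frailty and within-hospital analysis, the 10-point figures (A, B) are 19% and 43% for VFD-28, 35% and 5% for survivor duration, and 6% and 20% for the extubation hazard.

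VFD-28 therefore moves in both cases. Survivor duration holds its level only in B, and the extubation hazard only in A.

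**The case against.** The strongest reply is that the planned set already shows the problem. Death is modelled beside VFD-28 and mortality endpoints are listed, so a reader would see falling VFD-28 next to rising mortality. Under the assumed rates a VFD-28 signal with no mortality signal is rare, at 0.2% to 4.9% of studies. This largely stands and limits the harm. It is weaker for small differences. At a 5-point gap, mortality is detected in only about 40% of studies, and roughly 16% (1.4/9, case A) to 29% (4.9/17, case B) of the significant VFD-28 results come without a significant death difference. Nor does a mortality test show how much of a VFD-28 shift is due to death.

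A second reply is that the proposed extubation hazard is no cleaner, since it rejects in about 24% of studies in case B. That is correct. A reader might infer that it should replace the planned endpoints, but the check does not support this: which measure holds its level depends on a death mechanism that the documents cannot settle. It belongs beside them.

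Third, the outcomes named in Section 7 are examples, so survivor duration may well be analysed with the linear model. This is a fair reading, but such a model still conditions on survival.

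Finally, a reader might infer that new data are needed. Section 5.4.3 heads its follow-up block with status at days 7, 28 and 90, and intubation status with extubation date stands in that block. It can be read as recorded at each of those days, so the documents do not show that a further field is required.

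**Conclusion.** The gap is real and of minor to moderate weight. The duration objective rests on a composite and a survivor subset, and no named model treats death as a competing event. For a setting that affects death only, with a 10-point gap, the shift is about -0.8 to -1.3 days in VFD-28. In survivor duration it is about -1.9 days (liberated by day 90) or 0, depending on the death mechanism. These sizes rest entirely on assumed rates, two stylised mechanisms and unadjusted comparisons.

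A reader might infer that the plan would produce false duration findings unnoticed, or that VFD-28 is an invalid endpoint. The documents do not support either. Mortality is analysed alongside, a 10-point gap would be detected in about 90% of studies, and VFD-28 remains a legitimate outcome for the wider aim. What is missing is an analysis that addresses extubation directly and a rule for reading the measures together.

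**What to change.** In Section 7, for the secondary objective in the second analysis step:

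- Add an analysis of time from start of invasive ventilation to extubation, with death while ventilated as a competing event and patients still ventilated censored at day 90.
- Report cause-specific hazard ratios for extubation and for death side by side, with cumulative incidence curves, and account for hospital clustering.
- Keep VFD-28 as a labelled composite that is not read alone as an effect on duration.
- Keep duration in survivors as supporting, and state the day on which survival is judged.
- State which recorded extubation counts as the event, using the intubation status and extubation date in the day 7, 28 and 90 follow-up block of Section 5.4.3.
- State that the extubation hazard, survivor duration and mortality are read together, since none isolates duration under every death mechanism. The simulation above need not go into the SAP.

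The cost is a little more analysis and the joint interpretation of two hazards. Sections 5.4.2 and 5.4.3 already collect intubation, extubation and death dates. For transferred patients the intubation date is recorded where possible, and days ventilated in the previous hospital are collected too. An extra field on reintubation or tracheostomy is optional. Section 5.3 offers an occasion for it: "Participating centers will be visited by researchers to collect data of included patients".

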## **8. ETHICAL CONSIDERATIONS**

### **8.1 Regulation statement**

This study will be conducted according to the principles of the Declaration of Helsinki (revision Fortaleza, Brazil, October 2013).

### **8.2 Recruitment and consent**

Since the proposed study concerns a service review, no research related interventions will take place. Therefore, no ethical concerns exist. As pseudo-anonymous data, which can no longer be attributed to a specific data subject will be used, there is no concern for informed consent.

### **8.3 Benefits and risks assessment, group relatedness**

This study does not result in any risk or burdens to patients.

### **8.4 Compensation for injury**

Not applicable.

## **9. ADMINISTRATIVE ASPECTS, MONITORING AND PUBLICATION**

### **9.1 Handling and storage of data and documents**

Subject data will be stored a pseudo-anonymized, which means that relating the individual data to identifiable patients would require disproportional effort. Used data as written in the case report form will not contain any identifiable or relatable data. All handling of personal data will comply with the General Data Protection Regulation and the 'Reuse of care data for the purpose of research' standard of the AMC.

### **9.2 Monitoring and Quality Assurance**

Not applicable.

### **9.3 Amendments**

Not applicable.

### **9.4 Annual progress report**

Not applicable.

### **9.5 Temporary halt and (prematurely) end of study report**

Not applicable.

### **9.6 Public disclosure and publication policy**

Not applicable.

